5. INVESTIGATIONAL PLAN

5.1. Study Design and Duration

This is a double-blind, placebo-controlled, randomised phase II study. Eligible subjects will be randomised to one of three treatment groups, receive study treatment and undergo endpoint evaluations. Follow ups are scheduled one and three days after treatment, 3 and 12 months.

The first 10 patients will be treated sequentially, e.g. only one patient is randomised at a time. The next patient will be randomised only once the first patient has completed visit 5 and no suspected unexpected serious adverse event has occurred. Prior to randomisation of a new subject, the Investigators must ensure that the patient randomised previously has completed visit 5 and not suffered a suspected unexpected serious adverse event. Once the first 10 patients have completed the sequential phase and the DSMB has recommended continuing the trial, parallel recruitment may start (see also section 1.3).

The study is conducted at a minimum of three study centres which will screen and recruit 150 eligible patients. During the recruitment period, each study centre is expected to provide the capacity and willingness to recruit at least 20 patients. There will be a competitive recruitment of patients, which means that some hospitals will enrol more than 20 patients and some less.

However, if a study centre randomises less than 3 patients in 9 months, further recruitment of patients may be stopped because the quality of a study is dependent on the number of patients per centre. Very few patients in a centre might be related to a higher rate of missing data or patient visits and a higher withdrawal rate.

The centres should have solid experience in clinical research and profound knowledge of GCP. Moreover, participating Investigators should have special interest in studying patients with carotid stenosis.

5.2. Study Population

It is imperative that subjects fully meet all eligibility criteria.

5.2.1. Inclusion Criteria

For entry into the study, the following criteria **MUST** be met:

1) Signed written informed consent

2) Target population

a) Diagnosis:

- Extracranial carotid artery stenosis (diagnosed by vascular duplex ultrasound peak flow or angiography)
 - Lesions with $\geq 50\%$ stenosis according to the European Carotid Surgery Trial (ECST) criteria
- TIA, amaurosis fugax or stroke within the last 30 days

b) Age and sex: Men and women aged >18 years

Women of childbearing potential (WOCBP) must be using an adequate method of contraception to avoid pregnancy throughout the study and for up to 4 weeks after receiving investigational product in such a manner that the risk of pregnancy is minimised.

WOCBP include any female who has experienced menarche and who has not undergone successful surgical sterilisation (hysterectomy, bilateral tubal ligation, or bilateral oophorectomy) or is not postmenopausal. Post menopause is defined as:

- Amenorrhea ≥ 12 consecutive months without another cause or
- For women with irregular menstrual periods and on hormone replacement therapy (HRT), a documented serum follicle stimulating hormone (FSH) level > 35 mIU/mL

Women who are using oral contraceptives, other hormonal contraceptives (vaginal products, skin patches, or implanted or injectable products), or mechanical products such as an intrauterine device or barrier methods (diaphragm, condoms, spermicides) to prevent pregnancy, or are practicing abstinence or where their partner is sterile (e.g. vasectomy) should be considered to be of childbearing potential. WOCBP must have a negative serum or urine pregnancy test (minimum sensitivity 25 IU/L or equivalent units of HCG) within 72 hours prior to the start of study intervention.

5.2.2. Exclusion Criteria

Subjects must not be included for any of the following reasons:

1) Sex and reproductive Status:

- WOCBP who are unwilling or unable to use an acceptable method to avoid pregnancy for up to 4 weeks after receiving investigational product.
- Women who are pregnant or breastfeeding
- Women with a positive pregnancy test on enrolment or prior to investigational product administration.

2) Target disease exceptions

- NIHSS score > 18
- Recent intracerebral haemorrhage by X-ray computed tomography (CT) or nuclear magnetic resonance (NMR)
- Cardiac cause of embolisation (atrial fibrillation or other cardiac source e.g. artificial

heart valves)

3) Medical history and concurrent disease

- History of hypersensitivity, contraindication or serious adverse reaction to inhibitors of platelet aggregation, hypersensitivity to related drugs (cross-allergy) or to any of the excipients in the study drug
- History or evidence of thrombocytopenia ($<30.000/\mu\text{l}$), bleeding diathesis or coagulopathy (pathological international normalised ratio (INR) or activated partial thromboplastin time (aPTT))
- Thrombolysis within the last 48 hours
- Relevant haemorrhagic transformation as determined by CT, NMR or anamnesis
- Oral anticoagulation or dual anti-platelet therapy with aspirin or clopidogrel and other P2Y inhibitors at screening (3 days for dipyridamole extended release; 8 hours for tirofiban/Aggrastat)
- Sustained hypertension (systolic BP >179 mmHg or diastolic BP >109 mmHg), hypertensive patients shall be treated in accordance with current guidelines for the management of arterial hypertension
- History of severe systemic disease such as terminal carcinoma, renal failure (or current creatinine >200 $\mu\text{mol/l}$), cirrhosis, severe dementia, or psychosis
- Current severe liver dysfunction (transaminase level greater than 5-fold over upper normal range limit)
- Active autoimmune disorder such as systemic lupus erythematosus, rheumatoid arthritis, vasculitis or glomerulonephritis
- Known atrial fibrillation or other clinically significant ECG abnormalities (at present)

4) Other Exclusion criteria

- Inability to provide informed consent (except for patient's legally responsible representative)
- Acoustic window that does not allow for TCD recording
- Participation in any other interventional study within less than 30 days prior to screening
- Suspected poor capability to follow instructions and cooperate
- Prisoners or subjects who are involuntarily incarcerated
- Subjects who are compulsorily detained for treatment of either a psychiatric or physical illness (e.g. infectious disease)
- Ongoing drug or alcohol abuse

5.2.3. Discontinuation of Subjects from Treatment or study participation

If a subject was withdrawn before completing the study, then the reason for withdrawal must be entered on the appropriate case report form (CRF) page.

Subjects will be withdrawn from the study for the following reasons:

- withdrawal of consent by the subject for any reason at any time
- if continued study participation is not in the best interest of the subject, as judged by the Investigator (e.g. due to clinical adverse event (AE), laboratory abnormality or intercurrent illness)

- Termination of the study by advanceCOR GmbH, regulatory authorities or ethics committee
- Subjects, who become prisoners, involuntarily incarcerated or compulsorily detained for treatment of either a psychiatric or physical (e.g. Infectious disease) illness

Patients who discontinue study participation prior to visit 6 for any reason will be invited to skip to follow up visit 6.

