6.4. Treatment Compliance

The study site must keep a record of all study medication dispensed or disposed off throughout the study no matter whether on purpose or accidentally. Subjects who are noncompliant to receiving study medication will be discontinued from study treatment and are offered a follow-up visit including all assessments scheduled for visit 3 and 5.

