7.2.7. Transcranial Doppler

Central Analysis & Test Run

Each study centre shall send a test dataset to the central core laboratory prior to starting patient recruitment. The core lab will notify the study centre and sponsor of successful completion of a test run. TCD recordings are to be sent to the following core lab for central analysis:

PD Dr. med. [name]
Facharzt für Neurologie
[name]
[name]
[contact]
[contact]

Central analysis will be performed for both TCD datasets recorded for each patient enrolled (i.e. visit 1 and 3).

There is no need for local analysis of TCD recordings. Both TCD recordings are analysed centrally only.

MES detection by TCD

TCD recordings will be made from the middle cerebral artery (MCA), via the trans-temporal route. Each TCD assessment is recorded for one hour as specified below.

All TCD recordings must be performed under similar conditions, i.e.:

- Same apparatus
- Same position of patient
- System settings

All recordings shall be performed with a DWL TCD machine with single-depth 2-MHz transducers. Standard settings should be used. Machine settings shall be adapted to harmonised consensus guidelines (Ringelstein et al., 1998) and agreed upon by all study centers. For TCD recording, patients are to be placed in a sitting or supine position. The MCS will be identified via transtemporal window and a transducer will be attached using a

standard headset. TCD signals are recorded for one hour. The total number of MES per hour will be analysed.

Spectral display and audio signals will be monitored acoustically and visually online by an experienced observer during all recordings. Audio and visual signals will be recorded onto suitable storage media for central analysis.

MES will be identified visually as predominantly unidirectional short-duration intensity increase accompanied by characteristic acoustic clicking, chirping or moaning sounds. A previously agreed threshold will be set at all participating study centres following validation by analysis of standard reference tapes. MES intensity will be measured in dB and be calculated as the ratio of peak intensity of MES divided by the intensity of the background signal. The same algorithm will be used throughout the study. Central offline analysis of all recordings will be performed using the same machine and same algorithm.

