### **6.2 Full Analysis Set**

For efficacy, all subjects who have had at least one dose of medication will be included in the ITT analysis. The ITT analysis is defined as the first line efficacy analysis.

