## **8. STATISTICAL ANALYSIS**

### **8.1 Disposition of Subjects and Withdrawals**

Patients without any documented application of any study medication (without any documented infusion) will be excluded from all statistical analyses, but will be displayed in all data listings.

- The disposition of patients with regard to
  - enrolment of 1st patient and last follow-up of last patient
  - the number of patients enrolled (=subjects who gave informed consent),
  - number of study centres
  - number of enrolled patients by study centre
  - the number and percent of patients who discontinued prematurely within the study period,
  - the number and percent of patients who completed the study by treatment group and study centres.

will be summarised by means of frequency tables.

- For patients with a premature discontinuation the frequency of reason for discontinuation due to
  - AE
  - SAE
  - Withdrawal of consent
  - Investigator decision
  - Death
  - Termination criterion arose: Specification
  - other

will be summarised by treatment group and study centres.

In addition, all treated patients who discontinued prematurely from the study treatment and/or the study (according to the corresponding CRFs) will be listed; at least the time-point of discontinuation and the main reason for discontinuation.

- Analysis population

Inclusion/Exclusion criteria will be listed in the individual listing of raw data

Adherence to the protocol will be described by

- number and percent of patients with at least one deviation from the protocol
- number and percent of patients with at least one major deviation from protocol
- number and percent of patients with major deviations from protocol by type of protocol deviation
- number and percent of patients adhering to each analysis population

using frequency tables

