#### **8.4.5 Clinical endpoints summarised cumulatively i.e. before treatment, before CEA, 1 day after CEA, at 3 months and at 12 months.**

For the following endpoints

- Rate of all cause death
- Rate of stroke-related death
- Any TIA or stroke including haemorrhagic stroke
- Rate of Myocardial infarctions and coronary re-intervention

the number of patients will be summarized by means of frequency tables. Groups will be compared using Fisher's exact test.

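### Dosed patients who leave early are routed past the post-treatment TCD and DWI on which they will still be analysed, and protocol 5.2.3 and 6.4 are not reconciled with each other or with the SAP

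*Protocol*

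**What the plan says.** **Leaving the study.** Protocol 5.2.3 lists the grounds for withdrawal. They include withdrawn consent and the case "if continued study participation is not in the best interest of the subject, as judged by the Investigator", for which an adverse event, a laboratory abnormality and intercurrent illness are given as examples. The follow-up offer is: "Patients who discontinue study participation prior to visit 6 for any reason will be invited to skip to follow up visit 6".

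**What Visit 6 contains.** Under protocol 7.1.6 it covers clinical outcome, NIHSS, modified Rankin, Barthel, ECG, laboratory tests, adverse events and antibodies. TCD is scheduled only at Visits 1 and 3, and DWI only at Visits 1 and 5 (protocol 7.1, 7.2.7, 7.2.9). Nothing states whether the Visit 7 call is kept after the skip.

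**Not taking the medication.** Protocol 6.4 says: "Subjects who are noncompliant to receiving study medication will be discontinued from study treatment". These patients "are offered a follow-up visit including all assessments scheduled for visit 3 and 5".

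**Replacement.** Protocol 6.1.8 allows a patient who did not complete Visit 5 to be replaced, by rejecting the randomisation.

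**Analysis.**
- SAP 6.2: "all subjects who have had at least one dose of medication will be included in the ITT analysis".
- SAP 8.1: "Patients without any documented application of any study medication (without any documented infusion) will be excluded from all statistical analyses", although they remain in the listings.
- SAP 7.3 fills missing Visit 3 and Visit 5 values for the primary analyses by last observation carried forward (LOCF) and equates this with non-response.
- SAP 8.4.5, for the clinical endpoints: "the number of patients will be summarized by means of frequency tables". Groups are compared by Fisher's exact test, with no stated rule for unknown status.

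**The concern.** Treatment is a single 20-minute infusion. Once it has been given there is nothing left to stop, and the remaining visits only collect data. A dosed patient who leaves stays in the full analysis set whatever happens next, so his or her post-treatment data are the data the analysis needs. The route in 5.2.3 does not seek them. Section 6.4 does seek them, from a group that includes patients the SAP will not analyse.

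A patient withdrawn for an adverse event or intercurrent illness may have left because of a stroke, a bleed or a perioperative problem. If so, the missing TCD, DWI and 12-month results are informative, and the amount missing can differ by arm. Part of this loss is avoidable, because the visits and the telephone call already exist.

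**Working it through.** No figure in the plan is disputed. The only related one, 150 patients as 3 × 50, is consistent. The check is a cross-reading, followed by illustrations whose inputs are assumptions.

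**1. What is lost, by time of leaving (dosed patient, 5.2.3 route)**

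| Leaves | TCD, Visit 3 | DWI, Visit 5 | Visit 6 | Visit 7 call | Full analysis set |
|---|---|---|---|---|---|
| before Visit 3 | lost | lost | invited | not stated | yes |
| between Visits 3 and 5 | recorded | lost | invited | not stated | yes |
| between Visits 5 and 6 | recorded | recorded | invited | not stated | yes |

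**2. How the two rules overlap**
- Full infusion, then leaves the study: 5.2.3 applies and the patient is analysed.
- Incomplete infusion: could fall under 6.4. An infusion is documented, so the patient is analysed.
- No infusion, stays in contact: 6.4 applies. Visit 3 and 5 assessments are offered, but the patient is excluded by SAP 8.1.
- No infusion, leaves the study: 5.2.3 and 6.4 could both apply, with different offers. The patient is excluded by SAP 8.1.

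**3. What the missing-value rule does, by endpoint**
- Reduction in microembolic signals (MES) from Visit 1 to Visit 3 (SAP 8.4.1): LOCF sets Visit 3 equal to Visit 1, so the patient is a non-responder. A patient with no signals at Visit 1 could not have responded anyway and loses nothing.
- Any signal at Visit 3 (SAP 8.4.1): a patient negative at Visit 1 stays negative, which is a favourable value.
- New DWI lesions at Visit 5 (SAP 8.4.4): if LOCF is applied literally, no lesion is new. That is also favourable, and at odds with counting the patient as a non-responder.

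The direction of any bias therefore depends on the endpoint.

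**4. Size (assumed inputs)**

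One patient is 1/50 = 2 percentage points of an arm.

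Responder endpoint: let a fraction d of an arm leave before Visit 3, and suppose leavers would have responded like the rest. The counted rate is (1 − d) × p.
- Equal d in both arms, true difference 20 points: d = 5%, 10%, 20% (2.5, 5, 10 of 50) gives 0.95 × 20 = 19, 0.90 × 20 = 18 and 0.80 × 20 = 16 points.
- Leavers in one arm only, true rate 40% in both: that arm shows 38%, 36% or 32%, a spurious difference of 2, 4 or 8 points.

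Twelve-month events: with e observed events and u patients of unknown status in an arm of 50, the arm's rate lies between e/50 and (e + u)/50, a width of u/50. For u = 1, 3, 5 the width is 2, 6, 10 points.

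Example: e = 4, u = 5, and two of the five had an unseen event.
- Complete follow-up: 6/50 = 12%.
- Everyone in the denominator: 4/50 = 8.0%.
- Known status only: 4/45 = 8.9%.
- Kaplan-Meier censored at last contact: about 8.0% to 8.9%, depending on when the five left.
- Bounds: 4/50 = 8% to 9/50 = 18%.

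Neither a known-status denominator nor censoring recovers 12%. Only collecting the data does, and the bounds show what is left uncertain.

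**The case against.** **Other sections already protect part of the data, and this stands.** Protocol 8.7 requires any death of a randomised patient to be reported. Section 8.3.1 collects all SAEs within 30 days of dosing, and 7.1 adds visits every four weeks while study-related toxicity persists. SAP 8.5.4 foresees adverse event reports from relatives and physicians. Visit 6 is exactly what 5.2.3 offers, and clinical outcome is cumulative (7.2.6), so a claim that 3-month events are undercounted is not supported. What remains exposed is TCD, DWI and later stroke, TIA and infarction.

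**The number affected may be small.** Visit 3 falls 2 to 46 hours after treatment, and patients are supervised for 24 hours (protocol section 2). The SAP also reports a low incidence of MES. This limits the TCD loss more than the DWI or 12-month loss.

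**Some loss cannot be prevented.** A patient who withdraws consent and refuses contact is lost under any wording.

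**Three stronger readings are tempting but not supported.**
- That follow-up is inverted between dosed and undosed patients. Section 5.2.3 covers any reason and any patient, 6.4 concerns stopping treatment rather than leaving the study, and it does not define noncompliance as receiving nothing.
- That the 12-month call is lost. This is inferred from silence; skipping to Visit 6 could mean rejoining the schedule there.
- That SAP 8.4.5 counts unknown patients as event-free. It states no denominator.

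**The study is exploratory**, with no formal hypothesis testing planned in the protocol. That lowers the stakes, but a biased estimate is no more useful for being descriptive.

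**Conclusion.** The point holds as a gap and a lack of reconciliation. No section says that post-treatment TCD or DWI is sought from a dosed patient who leaves before Visit 3 or Visit 5, or whether the 12-month call is kept. Yet that patient stays in the full analysis set. Sections 5.2.3 and 6.4 overlap and give different offers, and neither is tied to SAP 6.2, 7.3 and 8.1.

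The size cannot be derived, because the documents give no dropout or event rates. The firm figure is 2 percentage points per patient per 50-patient arm; the larger illustrations rest on assumed rates. That the bias differs by arm is likewise an assumption: it needs withdrawal related to outcome and unequal between arms. Deaths, early SAEs and the 3-month outcome are better protected than TCD, DWI and 12-month non-fatal events. The change is worth making because it is cheap and prevents avoidable missing data.

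**What to change.** **Protocol 5.2.3.** Leave the withdrawal grounds and the investigator's judgement unchanged. Replace the sentence about skipping to Visit 6. Any dosed patient who stops early and has not refused further contact should be invited to the remaining scheduled data collection, as far as able and willing: Visit 3 TCD, Visit 5 DWI and NIHSS, Visit 6 and the Visit 7 call. At the least, vital status and stroke, TIA and infarction status should be sought at 3 and 12 months. This concerns data collection only.

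**Protocol 6.4 and 6.1.8.** Reconcile both with the new sentence. Say which patients 6.4 means, and that a dosed patient who is replaced remains in follow-up and in the full analysis set.

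**SAP 8.4.5.** Report by arm the number with known status at 3 and 12 months and use it as an explicit denominator. Add a sensitivity analysis for patients of unknown status, such as the bounds shown above. Censored cumulative incidence may be added as a supplement, with a note that it does not remove bias from informative dropout.

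**Cost.** Amendment wording, a small SAP addition and some extra tracing by sites; no new visits. The SAP, dated June 2019, describes conduct largely in the past tense, so the protocol change may come too late for patients already followed. The SAP change remains possible before unblinding.

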5.2.4. Follow-up of Discontinued Subjects

If the reason for withdrawal is a serious Adverse Event (SAE), the Investigator will follow the case up to resolution and provide advanceCOR with a final report of this SAE or justify why no final report will be provided.

6. TREATMENT

6.1. Study Treatment

In this protocol, the investigational products are Revacept and placebo (phosphate buffered saline, 1% sucrose, 4% mannitol).

6.1.1. Noninvestigational Product

Other medications used in the study as support or escape medication for preventative, diagnostic, or therapeutic reasons, as components of the standard of care for a given diagnosis, are considered non-investigational products.

6.1.2. Supply of study medication

Manufacturing of drug substance and filling of IMP vials is subcontracted to Glycotope Biotechnology GmbH, Heidelberg, Germany. Labelling and release of drug product is conducted at advanceCOR GmbH, Martinsried, Germany. Investigational product will be sent to individual study sites after site initiation.

Additional IMP supplies will be sent to individual study sites upon request. Please ensure to contact the Monitor or Sponsor of the trial as soon as less than 10 doses of IMP remain, or earlier in case of high recruitment rates.

6.1.3. Identification, packaging and labelling of study medication

IMP will be supplied to each study centre in kit boxes. Each kit box contains three IMP vials that make up one dose of trial medication for one patient. Each of the three vials contains 16.7 ml of clear solution of either:

- Placebo (phosphate buffered saline (PBS), 1% sucrose, 4% mannitol) or
- 40 mg Revacept (2.4 mg/ml in PBS 4% mannitol, 1% sucrose)

